## 5.5 STRATEGIES FOR RECRUITMENT AND RETENTION

**Recruitment:** We will recruit from this sample of over 50,000 residents in the Raleigh/Durham/Chapel Hill, NC area who meet our race and BMI inclusion criteria through multiple recruitment channels: 1) advertisement on social media, 2) community partnerships, 3) university listservs, 4) medical practices, and 5) word of mouth. We also have community partnerships with local Black churches, local chapters of Historically Black Fraternities and Sororities (i.e. National Panhellenic Council), and Durham County Department of Public Health – our partnerships with these entities should help us achieve our recruitment goals.

At least 20 individuals will be enrolled in the pilot study.

**Retention:** At enrollment, we will ask for home and cell numbers, if it is OK to send text messages. We will also ask participants to provide contact information for an alternate contact (friend or family member) in case we are unable to reach them directly.

**Incentive:** Study visits were compensated with \$40 per visit and Skills training sessions \$20 per visit. This amount was to compensate for time and travel to study site. We do not think this compensation is coercive and think the rate is in line with what the IRB typically endorses.

## 6 STUDY INTERVENTION(S) OR EXPERIMENTAL MANIPULATION(S)

### 6.1 STUDY INTERVENTION(S) OR EXPERIMENTAL MANIPULATION(S) ADMINISTRATION

#### 6.1.1 STUDY INTERVENTION OR EXPERIMENTAL MANIPULATION DESCRIPTION

**Core Weight Loss Sessions:** All Family dyads will be asked to attend 7 in person behavioral weight loss group sessions over 3 months covering content on dietary change, physical activity and behavioral modification to lose weight. Participants will have lessons, set goals, and receive individual feedback on their progress. The theoretical underpinning of this component is the social cognitive theory.

**Family dyadic skills training:** Concurrently, the brief family dyadic skills training will include two 30 minutes sessions delivered by a counselor using a secure Zoom platform. The training provides skills that should optimize implementation of the recommendations, strategies, and tips provided in the behavioral weight loss core curriculum that has been adapted for family inclusion. To assess for differences between in-person and online skills training, families will be randomized to: **online and in-person delivery modes**. Session one will address strategies to improve cohesion, an important aspect of healthy family functioning. Research has shown greater cohesion has been associated with greater weight loss among Black adults. Session two will address communication and conflict; these are important in handling stressful events and have been identified as essential skills to target for family inclusion in behavioral weight loss interventions. The content for the sessions will be informed by the couples skills training from TEAM. The theoretical underpinning for this component is Interdependence and Communal Coping, Social Interdependence Theory, and Olson's Circumplex of Family Model of Family Functioning.

#### 6.1.2 ADMINISTRATION AND/OR DOSING

- The intervention will be given by trained research staff.
- For participants recruited from the Raleigh/Durham/Chapel Hill area, the intervention will be delivered in person and/or online:
  - In person, face-to-face group sessions visits, will be given at the UNC Center for Health Promotion and Disease Prevention, located at [name].

- The other session may be given in person or by online e.g., Zoom.
- We will encourage participants to take part in all sessions. However, a participant will not be dropped from the study based on session participation
- If a participant takes part in 70% or more of anticipated visits, we will consider this a “full-dose.”
- The intervention format for this study is group or dyad.

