## 3 OBJECTIVES AND ENDPOINTS

OBJECTIVES	ENDPOINTS	JUSTIFICATION FOR ENDPOINTS	PUTATIVE MECHANISMS OF ACTION
Primary			
Primary Aim: To test the feasibility of implementing and acceptability of an online family dyadic/couple skills	Feasibility will be measured by the number of participants who consent, and the percent of dyads that attend both sessions.  Acceptability will be measured by a satisfaction survey complete by both dyad members	Primary Outcome	
Secondary			
Secondary Aim: To explore the experience of administering a family dyadic/couple skills training online from a counselor perspective (i.e., facilitators, barriers, acceptability).			

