## 6.3 MEASURES TO MINIMIZE BIAS: RANDOMIZATION AND BLINDING

### Randomization

Participants will be randomized 1:1, to either:

- Group 1: TEAM (in-person family skills training);
- Group 2: TEAM Plus (on-line family skills training).

Randomized assignment will be done by using the randomization number generator in excel.

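### Does the 70% full-dose rule need changing because someone who attended no skills-training session can meet it?

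*Combined protocol and SAP*

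**What the plan says.** Section 6.1.2 gives the protocol's only attendance threshold: "If a participant takes part in 70% or more of anticipated visits, we will consider this a" full dose. The section does not define the anticipated visits and sets no separate minimum for either component. It adds that "a participant will not be dropped from the study based on session participation", so the threshold does not affect who stays in the trial.

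Section 6.1.1 describes two components. Dyads in both arms are asked to "attend 7 in person behavioral weight loss group sessions over 3 months". Alongside these, "the brief family dyadic skills training will include two 30 minutes sessions". Only the delivery mode of the second component is randomised: "To assess for differences between in-person and online skills training, families will be randomized to" online or in-person delivery. Section 6.3 names the arms accordingly, for example "Group 2: TEAM Plus (on-line family skills training").

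Section 3 makes "the percent of dyads that attend both sessions" part of the primary feasibility outcome, and Sections 8.1 and 9.1 repeat it. Sections 6.2.1 and 6.4 provide for attendance to be recorded session by session, with dates.

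**The concern.** The trial asks whether online skills training is feasible. An adherence label that can be earned without any skills training looks wrong for that purpose. A statement that some percentage of the online arm received the full dose would naturally be read as uptake of the online training, yet it could be true of people who had none.

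The label and the primary attendance endpoint can also disagree about the same dyad, in either direction. The units differ too: the label is per participant, while the endpoint is per dyad. If the label were used to form a per-protocol group, that group would not be defined by exposure to what was randomised.

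**Working it through.** **Inputs.** Threshold 70% (Section 6.1.2); 7 core sessions and 2 skills sessions (Section 6.1.1); Visits 1 to 7 plus a baseline and a post-assessment visit (Section 1.3). The plan gives no session count of its own to reproduce, so the check is direct counting.

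**Formula.** Visits needed = 0.70 × number of anticipated visits, rounded up. This is compared with what a person can reach with no skills session.

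| Reading of anticipated visits | Number | 70% | Needed | All 7 core, no skills | Met? |
|---|---|---|---|---|---|
| Core + skills | 9 | 6.3 | 7 | 7/9 = 77.8% | yes |
| Numbered visits only | 7 | 4.9 | 5 | 7/7 = 100% | yes |
| Numbered + baseline + post | 9 | 6.3 | 7 | 7/9 = 77.8% | yes |
| Core + skills + post | 10 | 7.0 | 7 | 7/10 = 70.0% | yes |
| Core + skills + baseline + post | 11 | 7.7 | 8 | 7/11 = 63.6%; with baseline 8/11 = 72.7% | yes, counting baseline |
| Skills only | 2 | 1.4 | 2 | 0/2 = 0% | no |

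Only the last reading rules out a full dose without skills training, and Section 6.1.2 does not say that.

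**How wide the mismatch is on the 9-visit reading.** The skills sessions are 2/9 = 22.2% of visits, below the 30% that may be missed, which suggests that missing both is always harmless to the label. It is not. Because 7 visits are needed, only 9 − 7 = 2 may be missed, and skipping both skills sessions uses up that allowance.

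- 7 core + 0 skills: 7/9 = 77.8%, qualifies.
- 6 core + 0 skills: 6/9 = 66.7%, fails.
- 6 core + 1 skills: 7/9 = 77.8%, qualifies.
- 5 core + 2 skills: 7/9 = 77.8%, qualifies.
- 4 core + 2 skills: 6/9 = 66.7%, fails, although the dyad can still be a success on the attendance endpoint.

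So the no-skills case is confined to people who attend every core session and skip both skills sessions. An arm with 100% full dose and 0% on the endpoint would need everyone in it to show that pattern. That is a logical bound, and the documents give no attendance data to suggest it is likely.

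**Where the label is used.** It appears once, in Section 6.1.2. The adherence section (6.4) does not cite it. Section 9.3 (analysis populations), 9.4.6 (interim), 9.4.7 (subgroups) and 9.4.9 (exploratory) are all marked not applicable. The safety and baseline summaries (9.4.4, 9.4.5) do not refer to it.

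**The case for a change.** The strongest case for a change is that the plan does not rule out a use for the label. Sections 9.4.1 and 9.4.3 point to 9.4.2, which points to itself, so a later analyst could take full dose as a per-protocol definition or report it as adherence by arm. With 20 participants randomised 1:1 there are about 20/2 = 10 per arm, so one misclassified person moves an arm's figure by 1/10 = 10 percentage points. Reporting the two components separately would be cheap, since attendance is already recorded for each session.

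Part of this stands. The denominator is undefined, the label does not measure exposure to the randomised component, and it can differ from the endpoint in both directions. But the harm needs a report or an analysis set that the documents do not plan. The thin analysis section is a gap in Section 9, as is the lack of an explicit statement that the endpoint will be shown by arm; rewording Section 6.1.2 would mend neither.

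The separate skills measure that a change would add is already the primary attendance endpoint. The separate core measure is what Section 6.1.2 already gives if the anticipated visits are the seven numbered ones: 5/7 = 71.4%.

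Nor is disagreement between the two measures a contradiction. The synopsis describes the intervention as the whole 3-month programme, core sessions and skills training together. A dose for that package can reasonably differ from attendance at one part of it. The participant-versus-dyad difference is real but has no consequence for a label that enters no analysis.

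**Conclusion.** The counting holds: on every overall-attendance reading tried, a participant with no skills session can be labelled full dose. On the 9-visit reading this happens only with perfect core attendance. No change to the plan follows, because there is nothing to gain. The label drives no endpoint, population, analysis or decision, and the quantity that matters, dyad attendance at both skills sessions, is already a primary outcome supported by per-session records. The effect on the primary result is zero.

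This rests on two assumptions: that the two sessions in the endpoint are the two skills sessions, which is the natural reading of the primary aim, and that the label is not later given an analytic role. If it is reported descriptively, a competent analyst would state the denominator, present it as programme attendance, and describe uptake of the randomised component by the existing endpoint.

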## 6.2 FIDELITY

### 6.2.1 INTERVENTIONIST TRAINING AND TRACKING

- Process data:
  - number of sessions attended (including dates of visits),
  - Visit weights (if available)
  - A proportion (20%) of skills training will be audio-recorded to ensure that the counselor is correctly conducting the training as per the protocol

## 6.3 MEASURES TO MINIMIZE BIAS: RANDOMIZATION AND BLINDING

### Randomization

Participants will be randomized 1:1, to either:

- Group 1: TEAM (in-person family skills training);
- Group 2: TEAM Plus (on-line family skills training).

Randomized assignment will be done by using the randomization number generator in excel.

### Blinding Plan

As an open-label study, participants, providers, and many study staff will know to which group individual participants have been randomized.

## 6.4 STUDY INTERVENTION/EXPERIMENTAL MANIPULATION ADHERENCE

All session visits will be recorded. A session checklist will be completed by counselor at the end of every session.

The extent to which participants perform weight management behavioral skills and cognitive strategies will be assessed from questionnaire data addressing self-monitoring of weighing, dietary behaviors, and goal-setting.

## 6.5 CONCOMITANT THERAPY

For this protocol, participants may not use weight loss drugs. Medication usage will be assessed at each study visit and documented in the relevant Case Report Form (CRF).]

#### 6.5.1 RESCUE THERAPY

No rescue therapy outside of the study protocol is planned if participants do not lose weight.

### 7 STUDY INTERVENTION/EXPERIMENTAL MANIPULATION DISCONTINUATION AND PARTICIPANT DISCONTINUATION/WITHDRAWAL

#### 7.1 DISCONTINUATION OF STUDY INTERVENTION/EXPERIMENTAL MANIPULATION

The study intervention will not be discontinued unless the participant withdraws or is withdrawn as outlined in the above section.

If a participant withdraws or is withdrawn, no attempts will be made to collect follow-up measures.

If a participant requests to withdraw from the intervention but is willing to continue the measurement component of the study, he/she will be invited to continue with follow-up measures.

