### 1.2 SCHEMA

### 1.3 SCHEDULE OF ACTIVITIES

	Pre-screening (Pre-consent)	Consent/ Baseline (Pre- Visit 1)	Visit 1 Day 1 ±7	Visit 2 Day 7 ±7	Visit 3 Day 14 ±7	Visit 4 Day 21 ±7	Visit 5 Day 35 ±7	Visit 6 Day 49 ±7	Visit 7 Day 79 ±7	Post Assessment Day 91 ±7
Review Eligibility	X									
Informed Consent		X								
Demographics		X								
Clinical history		X								
Height		X								X
Outcome Evaluation										
Weight	X	X	X	X	X	X	X	X	X	X
Surveys	X									X
Randomization		X								
Control & Experimental Interventions		X	X	X	X	X	X	X	X	
Adverse Events Reporting	X				X	X	X	X	X	X

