#### 7.2 PARTICIPANT DISCONTINUATION/WITHDRAWAL FROM THE STUDY

Participants are free to withdraw from participation in the study at any time upon request.

Participants will be withdrawn according to protocol for the following reasons:

- Other medical diagnosis typically associated with significant weight loss (5% or more of body weight). In addition to malignancy, examples include nonmalignant gastrointestinal disease, endocrinopathies, infectious disease, rheumatologic diseases, etc. As [name] (study Co-I, general internist) will be blinded to participants' study group assignment, he will adjudicate in these situations, seeking consultation from medical colleagues as appropriate.
- New diagnosis of medical condition such that participation in a behavioral weight loss intervention is no longer appropriate.
- Permanent change in living situation (e.g. from home to nursing home) such that the participant has limited food options.

Pregnancy: Study participants who become pregnant may continue to participate in the study with the understanding that weight loss goals will be suspended during pregnancy through 3 months postpartum. If a pregnant participant wishes to continue with counseling session during pregnancy, the focus on counseling will be on dietary quality. The participant may resume full participation 3 months postpartum. Any data collected while the participant is pregnant will be censored and follow-up data will not be collected until the participant is 6 months postpartum.

A participant will be considered lost to follow-up if we are unable to contact him/her according to this algorithm.

- Attempts at telephone contact:
  - We will call up to 5 times over a 2 week period. We will attempt 2 calls during regular work hours (8:30 to 5:30 on weekdays) and 3 after hours, including Mon-Thurs evening between 5:31 and 9:00 pm and on Saturday calling between 8:30 and 5:30 pm.
  - We will leave up to 2 phone messages.
  - If no contact is made over this initial 2 week period as outlined above, we will undertake more limited contact attempts for an additional 2 weeks including up to 2 phone calls per week, 1 during business and the other during evening hours or on the weekend.
- Email: If a participant gives us permission to contact by email, we will send up to 4 weekly emails.
- Text: If a participant gives us permission to contact by text, we will send up to 4 weekly texts.

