## 8 STUDY ASSESSMENTS AND PROCEDURES

## 8.1 ENDPOINT AND OTHER NON-SAFETY ASSESSMENTS

Study data will be collected at baseline, and 3 months. Process data will be collected as part of the intervention via the web-based platform by counselors immediately after sessions.

OBJECTIVES	ENDPOINTS	JUSTIFICATION FOR ENDPOINTS	Collection Time (min)	Data Collection times (month)			
				0	1	2	3
Primary				X		X	X
Primary Aim: To test the feasibility of implementing and acceptability of an online family dyadic/couple skills	Feasibility will be measured by the number of participants who consent, and the percent of dyads that attend both sessions.  Acceptability will be measured by a satisfaction survey complete by both dyad members	Primary Outcome	1  15				X
Secondary			45				
Secondary Aim: To explore the experience of administering a family dyadic/couple skills training online from a counselor perspective (i.e., facilitators, barriers, acceptability).							X

- **Physical examination-based assessments (e.g., weight)**
- At study outset, weights (seven 50 pound weights) assessed and adjusted for accuracy on 12/3/19 by North Carolina Department of Agriculture and Consumer Services Standards Laboratory.

- Weights to be re-assessed and adjusted for accuracy annually.
- Scales tested for accuracy the first week of each month during their use in this study.

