### Collecting questionnaire data

- See Section 5.5, Strategies for Recruitment and Retention, which outlines how eligibility and baseline questionnaires will be administered.
- In brief, at the outset of the study, participants will complete questionnaires on-line using the qualtric interface.
- The data collection windows are 2 weeks before baseline, and 3 month follow-up.

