## 8.2 SAFETY ASSESSMENTS

As noted, this study is considered minimal risk. The following safety procedures are included as part of this protocol.

- As part of the physical activity intervention, an information sheet on safety while being active will be provided.
- A participant will be withdrawn from the study if they lose more than 15 lbs over the course of the month due to non-intervention protocol reasons. Participant will be instructed to contact their PCP to determine if additional evaluation is warranted for underlying medical disease that may be contributing to weight loss.

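### Section 7.1 leaves participants withdrawn by the study team with no route to the satisfaction survey, a primary outcome, even if they attended both skills sessions and are willing to answer

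*Combined protocol and SAP*

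**What the plan says.** Section 3 makes acceptability part of the primary aim: "Acceptability will be measured by a satisfaction survey complete by both dyad members".

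Section 7.1 sets the rule for people who leave: "If a participant withdraws or is withdrawn, no attempts will be made to collect follow-up measures". One exception follows. If the participant asks to stop the intervention but is willing to be measured, "he/she will be invited to continue with follow-up measures".

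Removal by the team is provided for in two places. Section 7.2 opens a list with "Participants will be withdrawn according to protocol for the following reasons" and gives three: a diagnosis typically associated with significant weight loss, a new condition that makes the program inappropriate, and a permanent change in living situation that limits food options. Section 8.2 adds a further rule, that people "will be withdrawn from the study if they lose more than 15 lbs over the course of the month due to non-intervention protocol reasons". Pregnancy is treated inconsistently: Section 8.3.9 rules out continuing, while Section 7.2 allows it.

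On timing, Section 8.1 says "Study data will be collected at baseline, and 3 months", and its questionnaire paragraph says "The data collection windows are 2 weeks before baseline, and 3 month follow-up". In the Section 1.3 schedule, the only mark after baseline in the surveys row is under "Post Assessment Day 91 ±7".

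**The concern.** The exception depends on who initiates the departure. A willing person who chose to leave the intervention is invited to be measured. An equally willing person whom the team removed is not. Removal by the team is not withdrawal of consent, and the listed reasons mostly concern weight interpretation or fitness for the weight-loss program. They need not prevent someone from rating two 30-minute sessions already attended.

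At stake are ratings from people who received the training being evaluated. That loss is avoidable, and it may be informative, because people removed for illness or a change in living situation may have experienced the training differently. The trial is very small and Section 7.2 plans no replacement, so each missing rating is a visible share of an arm.

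**Working it through.** The plan gives no figure on this point to reproduce. The check has a textual part and a short calculation of scale.

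**Is there another route to the survey?**

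1. The 7.1 rule covers both people who withdraw and people who are withdrawn. The exception requires a request from the participant, so it does not reach someone the team removes.
2. Sections 7.2 and 8.2 create such removals and offer no continued measurement.
3. The contact steps in 7.3 concern people who cannot be reached. They do not apply here.
4. Section 8.1 has counselors record process data right after sessions, and Section 6.2.1 lists these as attendance, visit weights if available, and audio recording of a portion of sessions. Satisfaction is not among them.
5. Under 8.3.9 a pregnant participant leaves the study, so the 7.1 rule would apply. Under 7.2 she is not withdrawn, although 7.2 postpones her follow-up data by a separate rule.

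**When is the survey given?** The schedule, the 8.1 text and the questionnaire windows all point to 3 months. The earliest date is Day 91 − 7 = Day 84. Two things leave doubt: none of these places names the satisfaction survey, and the endpoint table in 8.1 carries an unexplained mark that appears to fall at month 2. The skills sessions are not dated. They run alongside the core sessions, so finishing both before a later removal is possible, but how likely that is cannot be determined.

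**Scale of one lost survey.** Inputs: 20 participants (Sections 4.1 and 9.2), allocated 1:1. If 20 counts dyads, an arm has 10 dyads, or 20 people. If 20 counts individuals including partners, an arm has 5 dyads, or 10 people. The plan does not say which, nor whether the survey is scored per person or per dyad. Assumption: one removal by the team in the arm before the survey, with the partner still surveyed.

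With n units in the arm, the share with a complete survey is at most (n − 1)/n. If s of the n − 1 observed units are satisfied, the full-arm percentage lies between s/n and (s + 1)/n, a range of width 1/n.

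| Scoring | Dyads per arm | n | Complete, at most | Range from one unknown answer |
|---|---|---|---|---|
| Per person | 10 | 20 | 19/20 = 95% | 1/20 = 5 points |
| Per person | 5 | 10 | 9/10 = 90% | 1/10 = 10 points |
| Per dyad | 10 | 10 | 9/10 = 90% | 1/10 = 10 points |
| Per dyad | 5 | 5 | 4/5 = 80% | 1/5 = 20 points |

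**How likely is one removal?** The plan gives no withdrawal rate. Purely as assumptions, rates p of 2%, 5% and 10% per person among 20 people give 1 − (1 − p)^20 = 33%, 64% and 88% for at least one removal. These overstate the chance of the case at issue, which also requires that the person attended the training and is willing to respond.

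**The case against.** The strongest reply is that 7.1 draws a recognisable line: people who leave the study are no longer measured, and people who leave only the intervention may be. The affected group is narrow, because someone must attend, then be removed before about Day 84, and still be willing to answer. The triggers look uncommon over three months. No threshold or test depends on the result. All of this stands, and it limits the weight of the point. It does not explain why a willing person removed by the team should be treated differently from a willing person who asked to stop.

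It can also be said that giving the survey right after the second session would protect more ratings, including those lost to voluntary withdrawal or lost contact. That is true, but it moves the outcome's timing for everyone. The change proposed here affects only the people the rule now excludes.

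A reader might infer more than the documents support:

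- **That the survey is fixed at Month 3.** This is the best reading, but it is not stated. If the survey is given at month 2 or straight after the second session, much or all of the problem disappears.
- **That any change of address triggers removal.** The criterion is a permanent change in living situation that limits food options, with a nursing home as the example.
- **That the partner's survey is lost too.** Section 7.1 acts per participant and does not stop it, though it does not say that it continues.
- **That the attendance outcome is distorted as well.** Nothing removes withdrawn dyads from the attendance denominator, and attendance is recorded as sessions occur.

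**Conclusion.** The point holds as a low-cost improvement and does not undermine the design. As written, 7.1 excludes participants removed by the team from follow-up measures, and no other section offers them the satisfaction survey. The conclusion rests on the survey being given at the 3-month assessment. The sizes in the table are per event: they assume one removal in an arm, and the 20-point figure requires both the smaller arm and dyad-level scoring. Confidence is medium, because the survey's timing, the unit of scoring and the expected number of removals are all unstated.

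**What to change.** Add to Section 7.1:

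> A participant withdrawn by the study team who has not withdrawn consent will be invited once, optionally, to complete the satisfaction survey online or by phone at withdrawal or at Month 3, and the partner will still be surveyed.

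Record the date of each survey, and report by arm the number of dyads with two, one or no surveys.

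The cost is one sentence, the IRB review that any amendment needs, and one short survey per person affected (the 8.1 table appears to allow 15 minutes). Section 10.1.8 already plans online and phone collection, so no new visit, instrument or staff is needed. There are two downsides. It places a small burden on people who may be ill, which is why the invitation is optional and made once. Some surveys will also be dated before Day 84, which is why dates should be reported. The sentence does not settle the conflict between 7.2 and 8.3.9 on pregnancy; it covers a pregnant participant only if she is withdrawn. If data collection has already closed, the reporting by arm can still be done.
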